## **Secondary Outcome Measures**

- 1) Correlation between Intestinal Transit Time and constipation scores in MS patients with intestinal dysfunction. To calculate the Correlation Coefficient between Intestinal Transit Time and the Bristol Score, the Agachan-Wexner Score, the Cleveland Clinic Index, and the NBD Score.
- 2) Correlation between Diet and intestinal dysfunction in MS patients. To correlate the Intestinal Transit Time and the Bristol Scale Score to the type of diet usually followed by patients in terms of adequacy of caloric intake compared to BMI, composition of macronutrients, and dietary fibre intake.
- 3) Efficacy of TAI in MS patients with intestinal dysfunction. Compare the Scores of the assessment scales used before and after the 4-week TAI treatment period, in order to detect a reduction in severity and an improvement in QoL score. Calculate a possible advantage or non-benefit of the costs of treatment with TAI compared to the previous bowel management.
- 4) Analysis of Microbiota in MS patients with intestinal dysfunction, before and after treatment with TAI. Compare the composition of the intestinal microbiota of MS patients with the known "healthy"

profile of the Italian population of North East of Italy and assess any changes after the period of treatment with TAI.

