**Study Protocol**

MS (Multiple Sclerosis) is the most common neurological disease involving disabilities in young adults, with Central Nervous System involvement in both the brain and spinal cord. In a recent review, its incidence in the United Kingdom is estimated at 7 new cases per 100,00 inhabitants per year, with a prevalence of about 100,000 patients. Bowel symptoms, in particular constipation and faecal incontinence, affect more than two thirds of MS patients, and have a significant impact on patients' quality of life (QoL) by significantly limiting their social, occupational and emotional life.

Recently, bowel management based on Transanal Irrigation (TAI) has also been proposed in patients with MS, but TAI efficacy on intestinal transit time and patient's compliance with TAI have not been defined yet.

The primary objective of the study is to assess the prevalence, characteristics, severity and impact on the Quality of Life of intestinal disorders in patients who consecutively refer to the neurological clinic for the diagnosis and treatment of Multiple Sclerosis at Ferrara University Hospital, Italy.

Secondary objectives are to correlate the severity and characteristics of constipation and fecal incontinence with intestinal transit time and the type of faeces evacuated according to the Bristol Stool Form Scale; to evaluate the costs in terms of the precautions (diapers, traverses, drugs, medicated clysm, etc.) and the time dedicated to the evacuation, and how these items change in relation to the use of TAI; and finally, to study the composition of the intestinal microbiota in MS patients in relation to the type of bowel characteristics, comparing it with the profile of the healthy population of the same region of origin, Emilia-Romagna, Italy.

The study proposed is a monocentric prospective observational study. The study population will be composed of patients who will consecutively refer to the Neurological Clinics of the University Hospital of Ferrara, Italy for a number of about 150 patients.

The study will consist of two phases. The first phase will be the selection of eligible patients by administering two self-filling questionnaires: PacQol (Patient Assessment of Constipation Quality of Life) and NBD (Neurogenic Bowel Dysfunction Score).

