Patients with PacQol score  $\geq 32$  will be sent to the surgical clinic for the second phase. During the latter phase, patients will undergo a number of visits varying from 1 to 4 depending on the patient's willingness to continue the study. After the illustration of the purpose and protocol of the study to the patient,

classification of constipation and/or faecal incontinence in accordance with the Rome III Diagnostic Criteria will be assessed, with consideration of other possible etiopathogenetic factors other than MS. Further questionnaires will be filled in to evaluate the disease status (Constipation scoring system by Agachan-Wexner, Obstructed defecation score by Altomare et al, Fecal Incontinent grading scale by Jorge-Wexner); if the patient will consent to the continuation of the study, he will be given 7-days food diaries, evacuation diaries, radiopaque markers, stool collection container and appointment date for plain abdominal X-ray which may coincide with the appointment for examination number 2 (visit 2 or 3).

In particular, radiopaque markers Intestinal Transit Study will be performed according to the Bouchoucha procedure revised by Abrahamsson, which involves ingestion of 10 markers for 6 days at the same time and execution of a plain abdominal X-ray on the 7th day. During this week the patient will complete an evacuation diary recording the time and number of evacuations, the method of eventual bowel care, the consistency of faeces according to the Bristol Scale, any episode of fecal incontinence, the type of hygiene measures in general, the number of enemas, diapers, and any other garrison used in relation to the evacuation.

Patients will be asked to collect a faecal sample in a container during the last week before the following inspection at Visit 2.

During the second visit, the outcome of the plain abdominal X-ray will be discussed, the completed diaries will be collected, and the faecal sample will be stored at -20 C° and subsequently sent to the Laboratory of the Department of Pharmacy and Biotechnology of the University of Bologna, Italy for the analysis of the intestinal microbiome composition.

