Patients with severe NBD impairment will be offered the adoption of TAI as a way to manage their own evacuation, replacing any other measure used until that moment (suppositoires, enemas) with the exception of the possible intake of macrogols and/or prebiotics and/or probiotics which instead can be continued. This treatment will be proposed to all patients with severe impairment of intestinal function.

The TAI training with Peristeen will be carried out at the surgical clinic of the Surgical Department of the Ferrara University Hospital, Italy, by the personnel involved in the study, usually in a single session, but more sessions may be necessary.

During the following 4 weeks, patients will continue to use the Peristeen at home according to the instructions provided by the training staff collecting a stool sample each week. During the last of the four weeks of TAI use patients will repeat the compilation of food diaries, evacuation diaries, the radiopaque markers Transit Time, and collection of the stool for microbiota analysis. The appointment for the radiography could coincide also in this case with the following visit (visit 3 or 4).

During the last visit the outcome of Transit Time X-ray will be discussed, completed diaries and stool samples will be collected, and PAC-QoL questionnaire will be submitted to patients who completed the study pathway.

Patients will be asked about overall satisfaction of TAI treatment with Peristeen by means of a numerical assessment from 0 to 10.

Finally, any comment will be noted as well any events that might be related to TAI irrigation with Peristeen will be recorded.

Patients will undergo a neurological examination 3 months after the start of treatment.

The whole duration of the study will be of 2 years.

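### Secondary outcome 3 needs severity scores after TAI, but the visit narrative repeats only PAC-QoL, and no paired test is named for non-normal scores or proportions

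*Combined protocol and SAP*

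**What the plan says.** Secondary Outcome Measures, item 3, is the efficacy outcome for TAI. It asks the analyst to "Compare the Scores of the assessment scales used before and after the 4-week TAI treatment period, in order to detect a reduction in severity" and, as a separate aim, to show a better quality-of-life score. It also asks for a cost comparison.

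The Study Protocol section places the questionnaires in time. PAC-QoL and "NBD (Neurogenic Bowel Dysfunction Score" are completed at phase 1 selection. At the surgical clinic, "Further questionnaires will be filled in to evaluate the disease status": a constipation score, an obstructed defecation score and a "Fecal Incontinent grading scale". The baseline evacuation diary records, among other items, "any episode of fecal incontinence, the type of hygiene measures in general, the number of enemas, diapers".

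For the period after TAI starts, the same section says: "During the last of the four weeks of TAI use patients will repeat the compilation of food diaries, evacuation diaries", together with the marker transit study and stool collection. At the last visit it lists PAC-QoL for patients who finished the pathway, a 0 to 10 satisfaction rating, comments and TAI-related events. A neurological examination follows at 3 months, with no bowel scale named.

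The Statistical analysis section names Chi-square, Student's t and Mann-Whitney tests, to be used as appropriate, and a Cox model for predictors of improvement in bowel dysfunction after TAI.

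**The concern.** The outcome and the visit narrative do not match. The outcome treats severity and quality of life as two things to be shown. The narrative supplies a second questionnaire measurement only for quality of life. NBD is left out too, although the Study Protocol section ties the offer of treatment to it: "Patients with severe NBD impairment will be offered the adoption of TAI".

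If staff follow the narrative, the post-TAI severity scores are not collected, and they cannot be recovered later. The analyst would then have to choose a substitute for severity after seeing the data. The Cox model also needs a definition of improvement, and none is given on any measure.

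The one repeated questionnaire is also the one used for selection. Patients scoring at least 32 on PAC-QoL "will be sent to the surgical clinic for the second phase". In a comparison without controls, part of its change will be regression to the mean.

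The list of tests is a smaller matter. Pre/post data on the same patients call for within-patient methods. Of the named tests, only Student's t has a paired form.

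**Working it through.** **Step 1: trace each measure.** The plan states no figure to reproduce, so the check sets the schedule against the outcome.

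| Measure | Before TAI | After TAI (Study Protocol section) |
|---|---|---|
| PAC-QoL | Phase 1 | Last visit, completers |
| NBD | Phase 1 | Not listed |
| Constipation score | First surgical visit | Not listed |
| Obstructed defecation score | First surgical visit | Not listed |
| Incontinence scale | First surgical visit | Not listed |
| Transit time | Baseline week | TAI week 4 |
| Diary (stool form, incontinence episodes, enemas, diapers) | Baseline week | TAI week 4 |
| Satisfaction, 0 to 10 | None | Last visit |

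Questionnaires listed at both times: 1 of 5. Severity scales listed at both times: 0 of 4. Of the 3 primary and 4 secondary outcomes, 0 of 7 names the diary count of incontinence episodes. Enema and diaper counts could feed the cost comparison in item 3.

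**Step 2: what the repeated scales would give.** The documents state no SD, correlation or number of completers, so these are assumptions. Phase 2 is capped at 50 patients; 30 and 20 allow for patients who decline or drop out. Equal SDs before and after are assumed. The 95% CI half-width for a mean change, in SD units, is:

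- paired: t(0.975, n−1) × √(2(1−r)/n)
- treated as unpaired: t(0.975, 2n−2) × √(2/n)

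| n | Paired, r = 0.7 | Paired, r = 0.5 | Paired, r = 0.3 | Unpaired |
|---|---|---|---|---|
| 50 | 0.22 | 0.28 | 0.34 | 0.40 |
| 30 | 0.29 | 0.37 | 0.44 | 0.52 |
| 20 | 0.36 | 0.47 | 0.55 | 0.64 |

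For example, at n = 50 and r = 0.5: 2.01 × √(1/50) = 0.28, against 1.98 × √(2/50) = 0.40 unpaired.

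**Step 3: the diary, if reported.** For the net change in the proportion with any episode, the half-width is 1.96 × √((p1 + p2 − (p1 − p2)²)/n), where p1 and p2 are the proportions changing each way. With assumed values of 15% and 5% and n = 50: 1.96 × √((0.20 − 0.01)/50) = 0.12, or 12 points. It is 16 points at n = 30 and 19 at n = 20. Exact McNemar power in that case is 0.24, 0.10 and 0.03. This supports an estimate, not a test.

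**Step 4: regression to the mean in PAC-QoL.** If the top fraction f is selected on a normal score with retest correlation r, the expected fall without treatment is (1 − r) × φ(c)/f SD, where c is the cut-off.

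- f = 1/3: φ(c)/f = 1.09, giving 0.33 (r = 0.7) or 0.11 (r = 0.9).
- f = 2/3: φ(c)/f = 0.545, giving 0.16 or 0.05.

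The assumed range is therefore 0.05 to 0.33 SD.

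**The case against.** The best reply is that outcome 3 is part of the plan too. By promising a pre/post comparison of scale scores, it presupposes that the scores exist at both times. The visit account is a narrative. It does not say that PAC-QoL is the only questionnaire, there is no schedule table, and the case report form mentioned under Intervention is not in the documents. This stands to the extent that a reader might infer that the scales will certainly not be repeated, or that a severity result is impossible; the documents do not support either. They do show that the one place listing post-TAI collection in detail omits what the outcome needs. Reading the outcome as covering only scales used at both times does not help, because then only PAC-QoL qualifies and severity has no scale.

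A reader might also infer that the evidence on TAI would rest on PAC-QoL and costs alone. It would not: transit time, stool form, the rest of the diary and the microbiota are also repeated, and microbiota change is its own outcome. Outcome 3 simply does not name transit time or the diary measures.

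Nor is leaving diary incontinence episodes out of the outcomes an error. Recorded items need not be formal outcomes, the data would exist at both times, and a single-week measure has low power.

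On testing, use as appropriate, together with a possible paired t-test, means that the documents do not show unpaired tests will be used. What remains is that no paired test is named for non-normal scores or for proportions.

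Finally, repeating the scales does not cure regression to the mean. Measures correlated with PAC-QoL regress as well, though less, and NBD may itself be a selection variable: the Study Protocol section bases the offer of TAI on it, while the Intervention section uses PAC-QoL.

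**Conclusion.** The concern holds as an inconsistency between one secondary outcome and the visit narrative. By count from the documents, 1 of 5 questionnaires and 0 of 4 severity scales are listed after TAI. The severity half of outcome 3 therefore has no scale data on the plan as written, subject to what the case report form contains. The missing paired tests are a lesser point.

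The count rests on the text alone. The precision, power and regression-to-the-mean figures rest on assumed correlations, rates, selection fractions and completer numbers; they show scale and do not establish the defect. The primary aims, prevalence and characteristics, are untouched. The correction should still be made, because item 3 is the outcome that asks whether TAI improves symptoms and quality of life, and a score not taken at the last visit is lost.

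**What to change.** 1. Study Protocol, last visit, add: *The NBD, constipation, obstructed defecation and incontinence scales are repeated together with PAC-QoL.* If the case report form already has them, this sentence brings the protocol into line.
2. Statistical analysis, add: *All before/after TAI comparisons are within-patient (paired t-test or Wilcoxon signed-rank for scores and counts, McNemar for proportions).*
3. Optional, outcome 3: *The within-patient change in diary incontinence episodes, baseline week to TAI week 4, is reported descriptively with a 95% CI, as an estimate and not a powered test.*

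The cost is four short questionnaires, a few minutes each patient, at a visit that already takes place, plus a few sentences of text. No new visit or diary item is needed. The report should still say that the comparison is uncontrolled and that changes in selection variables include regression to the mean.

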## **Study population**

The study population will be composed by 150 MS patients who will consecutively refer to the MS Outpatient Neurology Clinic at Ferrara University Hospital, Italy. The PAC-QoL questionnaire will be given to every patient. This questionnaire is a self-filled instrument validated and used in various studies to document the consequences that intestinal disorders and defecation have on everyday life. The first 50 patients with a PACQoL score  $\geq 32$  will be asked to be willing to enter the next phase of the study that continues at the Coloproctological Outpatient Clinic of Ferrara University Hospital, Italy with an appointment provided by the neurologist with a pre-established schedule (with written consent).

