## **Statistical analysis**

Data will be expressed as median (interquartile range – IQR 25-75) and mean  $\pm$  standard deviation according to distribution assessed by Shapiro-Wilk test. Categorical data will be presented as numbers. Data will be analysed using Chi-square, t-student, and Mann-Whitney tests as appropriate. Cox regression analysis will be employed to assess independent predictors of improvement of intestinal dysfunction after Transanal Irrigation (TAI). Significance will be considered for values of  $p < 0.05$ . Statistical analysis will be performed with IBM SPSS Statistics for Windows, Version 24.0 (IBM Corp. Armonk, NY: IBM Corp.). The report will comply with the strengthening the reporting of cohort studies.

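### The two microbiota comparisons have no multiplicity control and no paired test: if m taxa are tested in both at p < 0.05, about 0.1 × m false positives are expected when nothing differs

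*Combined protocol and SAP*

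**What the plan says.** Item 4 of the Secondary Outcome Measures sets two tasks. One is "Compare the composition of the intestinal microbiota of MS patients with the known" healthy profile of the regional population. The other is to "assess any changes after the period of treatment with TAI". The Study Protocol section adds a further aim, "to study the composition of the intestinal microbiota in MS patients in relation to the type of bowel characteristics".

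The Statistical analysis section is one paragraph covering every outcome. On tests it says: "Data will be analysed using Chi-square, t-student, and Mann-Whitney tests as appropriate". It adds Cox regression for predictors of improvement after TAI. On the threshold it says "Significance will be considered for values of" p < 0.05. It mentions no adjustment for multiple tests, no overall test of composition and no pairing, and it does not label the microbiota work exploratory.

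On sampling, the Study Protocol section has one stool sample stored at the second visit and sent to the laboratory "for the analysis of the intestinal microbiome composition". During the four weeks of TAI, patients continue "collecting a stool sample each week", and a collection for microbiota analysis is also mentioned in the last of those weeks. The analysis paragraph does not say which of these samples enters the before/after contrast. The second phase is offered to a limited group: "The first 50 patients with a PACQoL score" of at least 32.

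**The concern.** A microbiota composition is a set of abundances. The comparison tests named in the plan each handle one variable at a time, so the direct way to apply them to outcome 4 is one test per taxon, each judged at 0.05. Nothing in the text limits how many such tests are run or how the results are read together. A list of significant taxa could then appear even if neither multiple sclerosis (MS) nor TAI has any bearing on the microbiota, and a reader could not tell which entries were due to chance.

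The second gap concerns pairing. Before and after TAI are measurements on the same patients. Chi-square and Mann-Whitney are tests for independent groups, and the t-test is not said to be the paired form. If the two samples from a patient resemble each other, an independent-groups test wastes that information and may miss real changes.

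**Working it through.** **Inputs**
- Threshold: 0.05 for each test (Statistical analysis section).
- Comparisons: two (item 4 of the Secondary Outcome Measures). The further aim on type of bowel characteristics is left out of the count because its number of groups is not given.
- Number of taxa, m: not stated. A range of 5 to 200 is assumed here.
- Taxon-by-taxon testing is also an assumption, drawn from the tests listed.

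The plan gives no power, number of tests or overall error rate for this outcome, so it has no figure of its own to reproduce.

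**Formulas, with no true differences and each test at its nominal 5% level**
- Expected false positives: 0.05 × (number of tests). With 2m tests this is 0.05 × 2m = 0.1 × m. It holds whether or not the tests are correlated.
- Chance of at least one: 1 − 0.95^(number of tests). This needs independent tests.

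| Taxa m | Expected, one comparison | At least one, one comparison | Tests in both | Expected, both | At least one, both |
|---|---|---|---|---|---|
| 5 | 0.25 | 23% | 10 | 0.5 | 40% |
| 10 | 0.5 | 40% | 20 | 1.0 | 64% |
| 20 | 1.0 | 64% | 40 | 2.0 | 87% |
| 50 | 2.5 | 92% | 100 | 5.0 | 99.4% |
| 100 | 5.0 | 99.4% | 200 | 10 | >99.9% |
| 200 | 10 | >99.9% | 400 | 20 | >99.9% |

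Worked example for m = 5 in both comparisons: 0.05 × 10 = 0.5 expected, and 1 − 0.95^10 = 1 − 0.599 = 0.401.

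**When would there be several chance findings?** Take several to mean three or more. The binomial chance of three or more is 8% with 20 tests (m = 10), 32% with 40 (m = 20), 58% with 60 (m = 30) and 88% with 100 (m = 50). It first reaches one half at 54 tests, that is 27 taxa in both comparisons.

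**Limits of these figures.** Abundances within one community are related, and the same pre-treatment samples may serve in both comparisons, so the percentages are indicative. The expected counts assume that each test really has a 5% level. If an unpaired test were used on positively correlated before/after samples, its true level would be below 5%. That contrast would then give fewer false positives than shown, at the price of missing real changes.

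**Effect of Benjamini-Hochberg control.** When nothing differs, holding the false discovery rate at 5% within a comparison also holds the chance of any finding in it at 5%. Over two independent comparisons that is at most 1 − 0.95² = 9.75%, whatever m is.

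**The case against.** The strongest reply is that the documents never mention taxa, a taxonomic level or a diversity index. They speak of composition and of a profile, which could be compared with a single overall test. A reader might infer that several taxa would be declared different by chance. The text does not support that as a fact, because it depends on a number of taxa that is not given. With 10 taxa in both comparisons, one false positive is expected and three or more are unlikely.

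A reader might also infer that the plan rules out adjustment. It does not. It gives a threshold and a short list of tests, to be used where suitable, and an adjusted p-value below 0.05 would fit those words. Nor is the list complete: items 1 and 2 of the Secondary Outcome Measures call for correlations, and the analysis paragraph names no correlation method. The plan is silent on adjustment.

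Both replies limit the wording of the point but do not remove it. No alternative rule for the microbiota is written anywhere, and even five taxa in both comparisons give a 40% chance of a false finding if the tests are independent.

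A third objection stands in full. The healthy comparator is described only as a known profile. An overall composition test or a two-sample test per taxon needs data on individual healthy samples, which the documents do not promise. Any remedy for that comparison has to be conditional.

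Finally, this is one secondary outcome of a single-centre observational study, which limits how serious the point is.

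**Conclusion.** The point holds in a conditional form. For the microbiota outcome the plan offers univariate tests at a flat 0.05, with no multiplicity control and no stated pairing. If m taxa are tested in both comparisons at their nominal level and nothing truly differs, about 0.1 × m false positives are expected, from 0.5 at 5 taxa to 5 at 50. The matching chances of at least one, 40% and 99.4%, rest on independent tests. The number of taxa and the taxon-by-taxon approach are assumptions.

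It would go too far to say that outcome 4 cannot separate signal from chance at all: once m is reported, a reader can set the number of findings against 0.05 × m per comparison. It would also go too far to extend the point to the primary outcomes, which do not depend on the microbiota. The change should be made, because a better method is available for data already being collected.

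**What to change.** Add a paragraph on outcome 4 to the Statistical analysis section that does the following.

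1. Names the taxonomic level to be tested, and so the set of tests.
2. States which stool sample counts as after treatment, and what use is made of the other weekly samples.
3. For before versus after TAI, uses one overall composition test on a distance named in advance (for example PERMANOVA with permutations restricted within patient), followed by paired tests per taxon.
4. Applies Benjamini-Hochberg control at 5% within each comparison and reports q-values with the number of taxa tested.
5. For MS patients versus the healthy profile, applies the overall test and the taxon-level tests only if sample-level data for the healthy profile are available. Otherwise that comparison is reported descriptively, without p-values.

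Benjamini-Hochberg is a less strict choice than Bonferroni, which for 50 taxa in both comparisons would require 0.05 / 100 = 0.0005 per test.

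For the before/after contrast the cost is a paragraph of text and little computing, with no new patients, visits or samples. For the healthy comparison, the cost depends on whether the reference data can be obtained, which the documents do not settle. The statistical price is that fewer individual taxa will be called significant.
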